Appendix 2 Response Evaluation Criteria In Solid Tumor.....	97
Appendix 3 Toxicity Management Guidelines.....	98
Appendix 4 Run in phase.....	125

SYNOPSIS

Study title	A randomized, phase IIb study of adjuvant durvalumab plus regorafenib vs untreated control in stage IV colorectal cancer patients with no evidence of disease (NED): VIVA trial
Study phase	Phase IIb
Study design	Randomized, open-label, multicenter, crossover
Sponsor details	IRCCS Ospedale Policlinico San Martino
Principal investigator(s)	[name] IRCCS Ospedale Policlinico San Martino [name]
Countries	Italy
Centre(s)	35 (GISCAD)
Planned sample size (N)	182 patients 91 patients per arm (2 arms)
Planned study start/end dates	First Patient First Visit 2020 Q4 Last Patient Last Visit 2022 Q4 Study end date 2025 Q4
Recruitment period	24 months
Rational and Objectives	
To date, the introduction of new effective drugs, improvements in surgical and locoregional techniques and supportive care have led to a median overall survival of over 30 months in patients with metastatic colon-rectal cancer (CRC). Thanks to this survival prolongation, medical oncologists and patients are more and more attracted by the possibility to reach a non-evidence of disease (NED) state not only under the classical favourable condition of a single or double liver metastases, but also under the less favourable conditions of multiple metastases even at different sites and even after 2 or 3 lines of treatment, whenever the clinical course allows. Therefore, this population of stage IV NED patients is growing.
 
Previous studies showed that median relapse-free survival (RFS) ranges from 8 to 16-18 months in R0 patients, but up to 90% of these patients eventually relapse: hence, there is an unmet clinical need for effective systemic treatment to reduce the chances of recurrence in stage IV NED patients.
 
After curative resection, international guidelines suggest regimens like FOLFOX, CAPOX, capecitabine or 5-FU/leucovorin alone as potential “adjuvant” therapy, but no standard treatments have been established and active surveillance with no treatment is the standard of care, especially if the patient has received prior chemotherapy as it will be the case for most of our patient population.
 
A phase Ib trial (EPOC1603) tested safety and toxicity profile of Regorafenib combined with an immune-checkpoint inhibitor (ICI) (Nivolumab) in gastric and colorectal cancer. The rather promising results of the phase Ib study has been presented to the ASCO 2019 Annual Meeting, suggesting the activity of Regorafenib in combination with ICIs.
 
The combination of Durvalumab and Tremelimumab showed to prolong median overall survival by 2.5 months compared with best supportive care alone in patients with advanced treatment-refractory colorectal cancer (phase II Canadian Cancer Trials Group (CCTG) CO.26 study). However,

	
no data are available about the role of Durvalumab as adjuvant therapy together with a tyrosin-kinase inhibitor (TKI) like Regorafenib in CRC. Given the promising results of these drugs in the metastatic setting, the main objective of this study is to evaluate the efficacy (DFS) of Regorafenib plus Durvalumab versus untreated control in the adjuvant setting for stage IV NED CRC patients.


Design
	
Design
  
Control arm: no treatment. Crossover to Regorafenib + Durvalumab upon relapse Experimental arm: Regorafenib 90mg d1-21 q28 + Durvalumab 1500mg (Q4W) up to 1 year

Run-in phase
	
The combination of an immune-checkpoint inhibitor plus TKI anti-angiogenic agents has been extensively investigated in several trials (phase II and III) in different types of tumors, with no evidence of new safety signals. Although specific data are not available on the combination of durvalumab and regorafenib, we would not expect major toxicity issues.
 
The run-in phase will be conducted on the first 4 patients randomized to the experimental arm using a starting dose of 60 mg/die of Regorafenib (and fixed 1500 mg of Durvalumab), to be escalated after 2 months to 90 mg/die if < 2 patients report serious adverse events (SAE). If Regorafenib 90 mg/die is well tolerated for other 2 months (< 2 patients with SAE) the run-in phase will be closed with the dose of 90 mg/die. In case of > 2 patients report SAE with 90 mg/die, additional 4 patients will be enrolled and treated with the same dose of Regorafenib (90 mg/die) and if < 2 of them report SAE the run-in will be closed at 90 mg/die. Conversely, if > 2 patients report SAE the dose of Regorafenib will be reduced again to 60 mg/die and the run-in will be closed with Regorafenib 60 mg/die.
 
If during the first part of the run-in > 2 patients report SAE with Regorafenib 60 mg/die, additional 4 patients will be treated with Regorafenib 30 mg/die for 2 months and, in case of > 2 patients with SAE, the trial will be revised. In case of good tolerance of Regorafenib 30 mg/die (< 2 patients with SAE), additional 4 patients will be enrolled and treated with Regorafenib 60 mg/die: if > 2 patients will report SAE the run-in phase will be closed with Regorafenib 30 mg/die, instead if Regorafenib 60 mg/die will be well tolerated (< 2 SAE) this will be the final dose of the run-in phase.

Feasibility: need for crossover	
Any trial randomizing active treatments vs a no –treatment-control presents feasibility problems. In this setting, where the large majority of patients will relapse within a few months, randomizing to an inactive control vs the possibility of receiving entirely innovative treatments will constitute a prohibitive feasibility obstacle.
 
This may be overcome by offering the most innovative treatment (REGO DURVA) to patients randomized to control whenever they relapse. This will also provide an opportunity for the conduct of a “satellite” phase IIa trial among a patient population that should present very good conditions and with a not too bulky disease load. Because this crossover will not affect the primary endpoint of the study, this part of the study will be addressed and better specified only if the main protocol is approved. As to the amount of Durvalumab to be provided for this part, we may expect that 1/3 of patients will not be eligible for the cross over and we may postulate that among those starting palliative Durvalumab + Regorafenib, patients will receive a median of 4 months of therapy.

Primary Endpoint	
Disease-Free Survival (DFS) will be defined by Punt, JNCI 2007
 
In addition to the Punt definition, the following condition will be considered DFS event: Two consecutive increases in CEA levels above upper limit level (time gap decided by the clinical investigator but no longer than 30 days).

Secondary Endpoints	
 • 18-months Disease-Free Survival (DFS) • Adverse events and Toxicity • Overall Survival (OS) • Compliance to the experimental treatment.
Exploratory Endpoints	
 • Association of translational research data (ctDNA, NGS) with the outcomes
Main Inclusion criteria	
To be enrolled in this study each patient must meet all of the following criteria at the time of randomization:
 
 1. Signed ICF, after oral as well as written information; 2. ≥ 18 years; 3. Body weight >30 kg 4. Histologically confirmed diagnosis of colorectal adenocarcinoma; 5. Patients must be in NED after completion of any treatments for stage IV CRC, including resections, RFA; RT with or without neoadjuvant/adjuvant therapies or CR after chemotherapy; 6. Patients must be randomized within 10 weeks since the achievement of the NED state. Those who have also received adjuvant therapy following the locoregional treatment are still eligible, provided they are randomized within 4 weeks since the last chemotherapy cycle; 7. NED state ascertained by means of CT scan and/or PET scan and/or MRI scan;

	
 8. ECOG Performance Status ≤ 1; 9. Must have a life expectancy of at least 12 weeks 10. CEA within normal limits 11. No residual toxicity from previous chemotherapy; 12. Women of childbearing potential must use safe contraception. 13. Adequate organ and marrow function as defined below: Absolute neutrophil count $\geq 1.5 \times 10^9 /L$ 
 • Platelet count $\geq 100 \times 10^9/L$ • Haemoglobin ≥ 9.0 g/dL • Serum bilirubin ≤ 1.5 x institutional upper limit of normal (ULN). This will not apply to patients with confirmed Gilbert's syndrome (persistent or recurrent hyperbilirubinemia that is predominantly unconjugated in the absence of hemolysis or hepatic pathology), who will be allowed only in consultation with their physician. • Serum Creatinine ≤ 1.5 x ULN or measured creatinine clearance (CL) >40 mL/min or Calculated creatinine CL >40 mL/min by the Cockcroft-Gault formula (Cockcroft and Gault 1976) or by 24-hour urine collection for determination of creatinine clearance • AST (SGOT)/ALT (SGPT) ≤ 2.5 x ULN, or ≤ 5 x ULN in the presence of liver metastases

Main Exclusion criteria
	
A patient who meets any of the following criteria at the time of randomization will be excluded from the study:
 
 1. Participation in another clinical study with an investigational product during the last 4 weeks 2. Concurrent enrolment in another clinical study, unless it is an observational (non-interventional) clinical study or the follow-up period of an interventional study 3. Prior randomisation or treatment in a previous durvalumab clinical study regardless of treatment arm assignment. 4. Patients with microsatellite instability (MSI) or DNA Mismatch Repair Deficiency (dMMR) are not allowed. 5. Any form of systemic disease that, in the opinion of the Investigator, would make the subject unsuitable for the study (including autoimmunity) or would prevent compliance with the study protocol; 6. Any unresolved toxicity NCI CTCAE Grade ≥ 2 from previous anticancer therapy with the exception of alopecia, vitiligo, and the laboratory values defined in the inclusion criteria 
 a. Patients with Grade ≥ 2 neuropathy will be evaluated on a case-by-case basis after consultation with the Study Physician. b. Patients with irreversible toxicity not reasonably expected to be exacerbated by treatment with durvalumab may be included only after consultation with the Study Physician.

	
 7. Any concurrent chemotherapy, IP, biologic, or hormonal therapy for cancer treatment. Concurrent use of hormonal therapy for non-cancer-related conditions (e.g., hormone replacement therapy) is acceptable. 8. Major surgical procedure (as defined by the Investigator) within 28 days prior to the first dose of IP. Note: Local surgery of isolated lesions for palliative intent is acceptable. 9. History of allogenic organ transplantation. 10. Active or prior documented autoimmune or inflammatory disorders (including inflammatory bowel disease [e.g., colitis or Crohn's disease], diverticulitis [with the exception of diverticulosis], systemic lupus erythematosus, Sarcoidosis syndrome, or Wegener syndrome [granulomatosis with polyangiitis, Graves' disease, rheumatoid arthritis, hypophysitis, uveitis, etc]). The following are exceptions to this criterion: 
 a. Patients with vitiligo or alopecia b. Patients with hypothyroidism (e.g., following Hashimoto syndrome) stable on hormone replacement c. Any chronic skin condition that does not require systemic therapy d. Patients without active disease in the last 5 years may be included but only after consultation with the study physician e. Patients with celiac disease controlled by diet alone 11. Uncontrolled intercurrent illness, including but not limited to, ongoing or active infection, symptomatic congestive heart failure, uncontrolled hypertension, unstable angina pectoris, cardiac arrhythmia, interstitial lung disease, serious chronic gastrointestinal conditions associated with diarrhea, or psychiatric illness/social situations that would limit compliance with study requirement, substantially increase risk of incurring AEs or compromise the ability of the patient to give written informed consent. 12. History of another primary malignancy except for: 
 f. Malignancy treated with curative intent and with no known active disease ≥ 5 years before the first dose of IP and of low potential risk for recurrence g. Adequately treated non-melanoma skin cancer or lentigo maligna without evidence of disease h. Adequately treated carcinoma in situ without evidence of disease 13. History of leptomeningeal carcinomatosis 14. Mean QT interval corrected for heart rate using Fridericia's formula (QTcF) ≥ 470 ms calculated from 3 ECGs (within 15 minutes at 5 minutes apart) 15. History of active primary immunodeficiency 16. Active infection including tuberculosis (clinical evaluation that includes clinical history, physical examination and radiographic findings, and TB testing in line with local practice), hepatitis B (known positive HBV surface antigen (HBsAg) result), hepatitis C. Patients with a past or resolved HBV infection (defined as the presence of hepatitis B core
--	--

	
antibody [anti-HBc] and absence of HBsAg) are eligible. Patients positive for hepatitis C (HCV) antibody are eligible only if polymerase chain reaction is negative for HCV RNA.
 
17. Current or prior use of immunosuppressive medication within 14 days before the first dose of durvalumab. The following are exceptions to this criterion:
 
a. Intranasal, inhaled, topical steroids, or local steroid injections (e.g., intra articular injection)b. Systemic corticosteroids at physiologic doses not to exceed 10 mg/day of prednisone or its equivalentc. Steroids as premedication for hypersensitivity reactions (e.g., CT scan premedication) 
18. Receipt of live attenuated vaccine within 30 days prior to the first dose of IP. Note: Patients, if enrolled, should not receive live vaccine whilst receiving IP and up to 30 days after the last dose of IP.
 
19. Female patients who are pregnant or breastfeeding or male or female patients of reproductive potential who are not willing to employ effective birth control from screening to 90 days after the last dose of durvalumab monotherapy.
 
20. Known allergy or hypersensitivity to any of the study drugs or any of the study drug excipients.
 
21. Any condition that, in the opinion of the investigator, would interfere with evaluation of the study drug or interpretation of patient safety or study results.

--	--

Investigational Treatments	
Name - Dosage form - Dosage - Mode of administration - Schedule
 
 1. Regorafenib – film-coated tablets – 90 mg – orally – once daily for the first 21 days of each 28-day cycle, up to 1 year 2. Durvalumab – solution for infusion after dilution – 1500mg – IV – infusion every four weeks up to 1 year 
Patients in the durvalumab+regorafenib treatment group will receive 1500 mg durvalumab via IV infusion Q4W and 90 mg Regorafenib d1-21 q28 for up to a maximum of 12 months (up to 12 doses/cycles), confirmed disease progression, unacceptable toxicity, withdrawal of consent, or another discontinuation criterion.
 
(N.B If a patient’s weight falls to 30kg or below (≤ 30 kg), then the patient should receive weight-based dosing equivalent to 20 mg/kg of durvalumab Q4W after consultation between Investigator and Study Physician, until the weight improves to above 30 kg (> 30 kg), at which point the patient should start receiving the fixed dosing of durvalumab 1500 mg Q4W).

Justification of Sample Size	
The study is set up as an exploratory phase 2B trial with sufficient patient numbers to broadly explore the differences between the experimental arm regimen and the control group.
 
The randomization plan is 1 to 1. Patients will be stratified by center.
 
The main aim of this study is to estimate the effect of the experimental arm relative to control group on the endpoint of interest: disease-free survival. In view of the treatment setting, disease-free survival is considered as the most sensitive clinical endpoint.
 
The sample size is calculated according to a median DFS estimate of 6 months in the control group and to a forecast of 2 years duration of uniform accrual and 2 years of follow-up after the end of accrual. To achieve 90% power at a 0.05 two-sided significance level to detect a 40% fall in DFS event rate (corresponding to a median increase from 6 to 10 months), 172 patients have to be accrued and followed up for at least 2 years in order to achieve the requested 164 events (recurrences or deaths). Assuming an attrition rate of approximately 5%, a total of 182 patients (91 per arm) have to be randomized.

Statistical considerations	
All randomized patients will be included in the primary assessment of efficacy (the intention-to-treat population). Safety analyses will include all treated patients (randomized patients receiving at least one dose of study drug). A log-rank test, will be used to assess disease-free survival and overall survival. A Cox proportional hazards model will be used to calculate HRs and 95% CIs). Sensitivity analysis of disease-free survival will be also done with a restricted mean survival time approach that does not assume the proportional hazards model, as outlined by Anderson and colleagues.
 
For patients in the control group after progression, a cross-over is allowed. A descriptive summary of the duration of this crossover treatment (overall and from the time of initial progression) will be done. The proportions of patients achieving an objective response or disease control will be compared with a logistic regression model adjusted for relevant covariates. Effect on survival of regorafenib plus durvalumab regimen within this

	
crossover part of the study will be analyzed by means of proportional hazard time-depended analysis. Median disease-free survival will be calculated with the Kaplan-Meier method.
 
All statistical testing is two-sided at the nominal 5% significance level, with no adjustment for multiplicity. All patients who receive at least one regorafenib plus durvalumab dose will be included in the safety analysis.

Publication plan	
 - Timelines 2025 Q4 - Target Journals: Lancet, Lancet Oncology, JCO.

Table 1. SCREENING PHASE

	28 to 1 day before randomization ^d	
Informed consent	X	
Inclusion / Exclusion criteria	X	
General disease medical history	X	
Prior / Concomitant medications	X	
Complete physical examination	X	
ECOG PS	X	
Weight	X	
Vital Signs ^a	X	
12-lead ECG ^b	X	
Tumor imaging ^c	X	Must be performed within 10 weeks before D1C1. Tumor imaging can be accepted even if performed before the procedures to obtain NED status.
Hematology, chemistry, coagulation and pregnancy test ^d	X	
Biomarkers ^d	X	CEA and CA 19-9 must be on normal range
Histologic Confirmation	X	Only if surgery performed to obtain NED state, resection of the metastases must be R0

Table 2. Experimental arm

	From -7 days to Day 1 Cycle 1	Day 1 Cycle 1	Day 8, 15, 22 Cycle 1	Day 1 Cycle 2	Day 15 Cycle 2	Day 1 Cycle 3 and above up to 1-year (12 cycles)	QW12 from C1D1 (+/- 7 days)	End of treatment visit	Treatment discontinuation 30-days from last treatment or at initiation of other anticancer therapy (whichever occurs first)	Follow-up period ^g
Prior / Concomitant medications								X		X
Complete physical examination								X		X
Limited physical examination ^a		X	X	X	X	X				
ECOG PS		X	X	X	X	X		X		X
Weight		X		X		X				
Vital Signs ^a		X	X	X	X	X		X		X
12-lead ECG ^b								X		

Tumor imaging/ response assessments ^c							X	X		X
Hematology ^d	X		X	X	X	X		X		
Coagulation ^d	X							X		
Chemistry ^d	X		X	X	X	X		X		
Biomarkers ^d							X	X		X
Durvalumab Administration		X ^e		X ^e		X ^f				
Regorafenib Administration		X ^e		X ^e		X ^f				
AEs assessments	X		X	X	X	X		X	X	X
Survival and anti-cancer therapy									X	X

Table 3 - Control arm

	QW12 from C1D1 (+/- 7 days)	End of treatment visit	Treatment discontinuation 30-days from last treatment or at initiation of other anticancer therapy (whichever occurs first)	Follow-up period ^g
Prior / Concomitant medications	X	X		X
Complete physical examination	X	X		X
ECOG PS	X	X		X
Weight	X	X		
Vital Signs ^a	X	X		X
Tumor imaging/ response assessments ^c	X	X		X
Hematology ^d	X	X		X
Chemistry ^d	X	X		X
Biomarkers ^d	X	X		X
AEs assessments	X	X	X	X
Survival and anti-cancer therapy			X	X

Abbreviation: CBC: cell blood count; RBC: red blood cell; WBC: White blood cell; aPTT: activated partial thromboplastin time; PT: prothrombin time; INR: international normalized ratio; AST: Aspartate aminotransferase; ALT: alanine aminotransferase; LDH: Lactate dehydrogenase; β -hCG: beta-human chorionic gonadotropin; Na: sodium; K: potassium; Cl: chloride; Mg: magnesium; Ca: calcium; P: phosphate; CEA: Carcinoembryonic antigen; Ca 19-9: Carbohydrate antigen 19-9; ECOG PS: Eastern Cooperative Oncology Group Performance Status; ECG: electrocardiogram; AEs: adverse events

a) Vital signs and Physical examination

Patients will have a complete physical exam to include an examination of major body systems and an assessment for emergent toxicities or changes from prior visits. Limited physical examination should be performed symptom-directed.

Examinations will be conducted by a physician, trained physician's assistant, or nurse practitioner, as acceptable according to local regulation.

Vital signs include: blood pressure and heart rate, body temperature, respiratory rate.

b) Electrocardiogram (ECG)

Perform a 12-lead resting electrocardiogram (ECG) before the beginning of the treatment, at the end-of-treatment and if clinically indicated. Patients should be in a supine position for at least 10 min before recording. ECG tracings will be reviewed by a qualified physician for assessment of QT interval as well as signs of qualitative abnormalities, including evaluation of rhythm, ST segment morphology, T wave morphology, and presence/absence of U wave.

The original ECG tracing will be maintained in the source documentation of each patient.

c) Tumor imaging/ response assessments

Including computed tomography (CT) scan / magnetic resonance imaging (MRI) / PET scan. The same radiographic procedure should be used throughout the study for each patient.

Tumor assessment should be performed every 12 weeks \pm 1 week for the first year (relative to the date of randomization), every 16 \pm 1 week in the second year and then every 24 weeks \pm 1 week thereafter until RECIST 1.1-defined radiological PD or death (whichever comes first).

d) Local laboratory assessments will include the following:

- Hematology profile (CBC, including RBC count, hemoglobin, hematocrit, WBC count with differential [neutrophils, eosinophils, lymphocytes, monocytes, basophils] and platelet count)
- Coagulation profile (aPTT, PT, INR)
- Chemistry profile includes Na, K, Cl, Mg, Ca, P, blood urea nitrogen, creatinine, glucose, total protein, albumin, AST, ALT, alkaline phosphatase, total bilirubin, LDH, amylase, lipase
- Pregnancy test (a positive urine test will be confirmed with a serum pregnancy test) during the study (for woman of childbearing potential). If a patient becomes pregnant while in the study, the study treatment must be immediately discontinued. Pregnancy information for a female patient or for the female partner of a male patient should be reported within 24 hours from the time the Investigator first becomes aware of a pregnancy or its outcome.
- Biomarkers: CEA, Ca19.9, backup plasma sample.

Samples for hematology, serum chemistry, coagulation, pregnancy test and biomarkers will be analyzed at the study site's local laboratory. Investigator may have additional blood tests performed for the purpose of planning treatment administration, dose modification, or following AEs.

Procedure does not have to be repeated if performed within 72 hours prior to Cycle 1 Day 1 (i.e. first day of dosing)

- e) The first administration of Regorafenib + Durvalumab must be done within 10 weeks from NED state. Patients who are rendered NED and have received an adjuvant program are still eligible, provided they are randomized within 1 month since the last chemotherapy cycle
- f) Up to 1 year
- g) During the early follow up phase (Month 13-Month 24) all patients will undergo the following visit every 4 months. During the late follow up phase (Month 25 to Month 60) all patients will undergo the following visit every 6 months.

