2.9 Regorafenib and immune-checkpoints inhibitors

Regorafenib is approved treatments for previously treated mCRC patients. It is an oral multi-kinase inhibitor which targets angiogenic, stromal and oncogenic receptor tyrosine kinase (RTK) administered in numerous countries worldwide, including the United States and European Union.

It was found to exhibit potent inhibitory activity against angiogenic and stromal receptor tyrosine kinases (RTKs) VEGFR 1–3, tyrosine kinase with immunoglobulin and epidermal growth factor homology domain 2 (TIE2), fibroblast growth factor receptor 1 (FGFR1), and platelet derived growth factor receptor beta (PDGFR- β), in addition to oncogenic RTKs RET and KIT, and intracellular signaling kinases c-RAF/RAF-1 and BRAF.

It was approved based on a Phase III trial (CORRECT trial) that showed an improvement of OS compared to best supportive care of 1.4 months (6.4 versus 5 months, hazard ratio [HR] 0.77, 95% CI 0.64-0.94) and a PFS of 0.2 months (HR 0.49, mPFS 1.9 versus 1.7 months) (Grothey et al. 2013). These results were later confirmed by a smaller Phase III, randomized, double-blind, placebo-controlled trial conducted in Asia (CONCUR) (Li et al. 2015).

As the approved dose of regorafenib (160 mg daily for 21 days of every 28-day cycle) may be too high for many patients it was conducted the phase II ReDOS trail. It demonstrated that a weekly dose escalating strategy (starting with 80 mg daily, escalating weekly in the absence of treatment-related toxicity to a target of 160 mg daily) allows more patients to continue therapy beyond the first response assessment compared with starting at 160 mg per day. In a preliminary report, presented at the 2018 American Society of Clinical Oncology (ASCO) Gastrointestinal Cancers Symposium, median overall survival also trended better in the dose escalation cohort (9 versus 5.9 months), and toxicity was more favorable. (Bekali-Saab T et al. 2018)

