4.3 Study plan

Approximately 182 patients, >18 years of age, with Stage IV CRC and no evidence of disease (NED) will be enrolled. Randomization will be 1:1.

Prior to enrolment, all patients will have received standard of care (SoC) treatment for Stage IV CRC (locoregional), and will have to be NED.

Treatment schedules and safety and efficacy assessments will be the same for all patients, regardless of treatment group.

All patients will undergo assessments (Section 6.2) to confirm compliance with inclusion and exclusion criteria, after that they will sign informed consent. Patients who will be randomized to the experimental treatment group will receive up to 1 year of regorafenib plus durvalumab.

Run-in phase: The combination of an immune-checkpoint inhibitor plus TKI anti-angiogenic agents has been extensively investigated in several trials (phase II and III) in different types of tumors, with no evidence of new safety signals. Although specific data are not available on the combination of durvalumab and regorafenib, we would not expect major toxicity issues.

Therefore, a run-in phase will be conducted on the first 4 patients randomized to the experimental arm using a starting dose of 60 mg/die of Regorafenib (and fixed 1500 mg of Durvalumab), to be escalated after 2 months to 90 mg/die if < 2 patients report serious adverse events (SAE). If Regorafenib 90 mg/die is well tolerated for other 2 months (< 2 patients with SAE) the run-in phase will be closed with the dose of 90 mg/die. In case of > 2 patients report SAE with 90 mg/die, additional 4 patients will be enrolled and treated with the same dose of Regorafenib (90 mg/die) and if < 2 of them report SAE the run-in will be closed at 90 mg/die. Conversely, if > 2 patients report SAE the dose of Regorafenib will be reduced again to 60 mg/die and the run-in will be closed with Regorafenib 60 mg/die.

If during the first part of the run-in > 2 patients report SAE with Regorafenib 60 mg/die, additional 4 patients will be treated with Regorafenib 30 mg/die for 2 months and, in case of > 2 patients with SAE, the trial will be revised. In case of good tolerance of Regorafenib 30 mg/die (< 2 patients with SAE), additional 4 patients will be enrolled and treated with Regorafenib 60 mg/die: if > 2 patients will report SAE the run-in phase will be closed with Regorafenib 30 mg/die, instead if Regorafenib 60 mg/die will be well tolerated (< 2 SAE) this will be the final dose of the run-in phase.

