7.1 Treatment Administered

Patients randomized and assigned to experimental arm will receive Regorafenib + durvalumab. Treatment will begin only after the patient has been randomized to the Treatment Group. Regorafenib 90 mg will be administered orally once daily for the first 21 days of each 28-day cycle, up to 1 year. Durvalumab (1500mg q4W IV infusion) will be administered every four weeks up to 1 year.

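### On its direct branch the run-in can close at 90 mg regorafenib with no patient having started at 90 mg, the starting dose that the treatment sections then give

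*Combined protocol and SAP*

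**What the plan says.** The run-in rule appears in the same form in the synopsis, Section 4.3 and Section 7.1.1. The cohort is defined by "The run-in phase will be conducted on the first 4 patients randomized to the experimental arm", who begin "using a starting dose of 60 mg/die of Regorafenib (and fixed 1500 mg of Durvalumab), to be escalated after 2 months to 90 mg/die" if fewer than 2 of them have an SAE. The closing condition is then: "If Regorafenib 90 mg/die is well tolerated for other 2 months (< 2 patients with SAE) the run-in phase will be closed" at 90 mg.

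The other route to 90 mg opens with "In case of > 2 patients report SAE with 90 mg/die". Four additional patients are then enrolled and treated at 90 mg, and the run-in closes at 90 mg if fewer than 2 of these have an SAE. No 60 mg lead-in is described for them. Other branches close the run-in at 60 mg or 30 mg.

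For treatment in general, Section 7.1 states: "Regorafenib 90 mg will be administered orally once daily for the first 21 days of each 28-day cycle, up to 1 year". The synopsis gives the same regimen, and Table 5 in Section 7.2 lists 90 mg as the starting dose. None of these mentions a lead-in or makes the dose depend on the run-in result.

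Two background sections bear on starting dose. Section 2.9 describes a trial of regorafenib in which weekly escalation from 80 mg towards 160 mg "allows more patients to continue therapy beyond the first response assessment compared with starting at 160 mg per day". Section 2.11 says, for regorafenib with a PD-1 inhibitor, that most patients could not sustain a 120 mg start, while some who started at 80 mg could go up to 120 mg.

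**The concern.** A run-in supports the regimen that its patients received. On the direct branch the four patients reach 90 mg after two months on both drugs, and the cohort moves up only if it had fewer than 2 SAEs at 60 mg. Later patients, following Section 7.1, would meet 90 mg and durvalumab together on Day 1. The protocol's own background treats the starting dose as relevant to tolerability, so the two exposures cannot be assumed equivalent.

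The timing also differs. With 28-day cycles, the run-in's 90 mg period falls at about cycles 3 and 4. Direct starters take 90 mg in cycles 1 and 2, which Section 8.1.2 follows most closely (weekly visits, then two-weekly, then monthly).

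At stake is what the finding of good tolerance can be taken to mean, in a run-in that Sections 4.3 and 7.1.1 introduce by saying that specific data on the combination are not available.

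**Working it through.** The plan states no operating characteristic for the run-in, so it has no figure to reproduce. The check has two parts.

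**Exposure judged against exposure given**

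| Route to closure at 90 mg | Who is judged | Anyone started at 90 mg? |
|---|---|---|
| Direct: fewer than 2 of 4 with an SAE at 90 mg | Same four patients, after 2 months at 60 mg | No |
| Expansion: more than 2 of 4, then fewer than 2 of 4 new patients | Four additional patients | Yes, as written |
| Given afterwards (synopsis, 7.1, Table 5) | Later experimental-arm patients | Yes, no lead-in stated |

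**How often each route is taken**

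Inputs: cohorts of 4 and the thresholds, from the run-in text. The two-month SAE risk *p* at 90 mg is not in the documents. It is assumed to be 20%, 30% or 40% and the same in both cohorts. All figures are conditional on having passed the 60 mg step.

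- Direct closure: P(X < 2) = (1−p)^4 + 4p(1−p)^3
  - p = 0.20: 0.4096 + 0.4096 = 0.819
  - p = 0.30: 0.2401 + 0.4116 = 0.652
  - p = 0.40: 0.1296 + 0.3456 = 0.475
- Expansion triggered: P(X > 2) = 4p^3(1−p) + p^4 = 0.027, 0.084, 0.179
- Closure through expansion: P(X > 2) × P(X < 2) = 0.022, 0.055, 0.085
- Direct share of all closures at 90 mg: 0.819/(0.819 + 0.022) = 97%; 0.652/(0.652 + 0.055) = 92%; 0.475/(0.475 + 0.085) = 85%

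The rule does not say what follows exactly 2 SAEs (probability 0.154, 0.265, 0.346). If that result also led to expansion, the direct share would be 85%, 74% and 66%. On either reading, and over this range, the direct branch is the usual way to close at 90 mg.

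**Effect of the 60 mg step**

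Reaching 90 mg requires passing both steps. With an assumed SAE risk of 20% at 60 mg and 20% at 90 mg after the lead-in, and the two steps taken as independent, the joint probability is 0.819 × 0.819 = 0.67. With 10% at 60 mg it is 0.948 × 0.819 = 0.78. Four direct starters with an assumed risk of 30% would pass a single step with probability 0.65. The contrast between escalated and direct-start cohorts thus depends heavily on the unknown 60 mg risk.

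**The case against.** Several points on the other side stand.

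- A reader might infer that 90 mg is only ever cleared in patients who first took 60 mg. The documents do not support that: the expansion branch treats four additional patients at 90 mg and can close on them.
- A reader might infer that every later patient, 91 − 4 = 87 of the experimental arm, will start at an untested dose. That figure holds only for direct closure at 90 mg, and the run-in may close at 60 or 30 mg.
- A reader might set 82% (20% risk after the lead-in) against 65% (30% risk in new starters) and infer a bias of known size towards passing 90 mg. That leaves out the 60 mg step, and every rate in it is assumed.
- Early toxicity is not wholly unobserved. SAEs in the first two months on both drugs, with durvalumab at its fixed dose, count at the 60 mg step. What is missing is early toxicity specific to a 90 mg start.
- There is some outside support. Section 2.11 argues for a 90 mg start from combination data at 80 and 120 mg, and Section 2.2 says that the combination proved safe in a French study, which conflicts with the run-in text. The trial in Section 2.9 used other doses and a weekly schedule, and no checkpoint inhibitor is mentioned.
- Direct starters are monitored. Section 4.2 provides a data-monitoring committee, Section 9.9 a review of each SAE, and cycle 1 has weekly visits.

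These points limit the size and reach of the concern but leave the mismatch in place. The committee's review is described only as periodic, with no timing and no link to direct starters. The Appendix 4 flowchart is not available here and could add detail.

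**Conclusion.** The point holds for the direct branch. There, the rule that closes the run-in at 90 mg judges a 60-then-90 mg sequence, while the treatment sections give a 90 mg start. If the run-in closes this way, its conclusion does not extend to early toxicity of starting at 90 mg. Separately, the treatment sections state 90 mg without condition, so a closure at 60 or 30 mg would contradict them.

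The size of any effect on safety cannot be taken from the documents. The pass probabilities of 82%, 65% and 48% are exact binomial results for assumed SAE risks of 20%, 30% and 40%, given that the 60 mg step has been passed. They describe how the rule behaves. They do not show that 90 mg is unsafe or how far a lead-in lowers the risk. This should be corrected, but it does not affect the primary efficacy analysis as planned.

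**What to change.** 1. Reconcile the run-in text (synopsis, 4.3, 7.1.1) with Section 7.1, Table 5 and the synopsis treatment entry, so that the exposure judged and the exposure given afterwards agree. Otherwise, state that the run-in conclusion applies only to the 60-then-90 mg sequence.
2. Carry the run-in outcome into the treatment sections, so that they remain correct whichever dose the run-in closes at.
3. In the safety analysis (Section 5.2.4), tabulate SAEs separately for escalated and direct-start patients.
4. Have the data-monitoring committee already planned in Section 4.2 review early SAEs in direct starters as one of its periodic reviews.

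No dose, threshold or stopping rule is proposed; those choices belong to the sponsor and the investigators. The cost is a wording amendment, one extra table and one timed committee review, with no added patients or procedures.
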